8.3.2.1. Worsening of Asthma during Exercise Challenge

Exercise challenges may be stopped at any time during the assessment for worsening asthma. Guidelines for treatment are provided in the SRM.

If a subject's FEV₁ decreases to $\geq 40\%$ from their pre-exercise FEV₁ following exercise challenge, he/she must receive rescue therapy. If he/she requires rescue therapy with anything other than MDI or nebulized albuterol/salbutamol or ipratropium (secondarily) following the exercise challenge assessment, he/she is not allowed to continue in the study (see Section 6.4.1).

The subject should not leave the clinic until FEV₁ returns to within 95% of the baseline FEV₁ target recovery value or the subject is judged medically stable by the investigator to leave the clinic.

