2. SUMMARY OF KEY PROTOCOL INFORMATION

2.1. Changes to the Protocol Defined Statistical Analysis Plan

There were no changes or deviations to the planned statistical analysis specified in the third amendment of the protocol (Dated: 25-MAY-2016) of study 201832 [GlaxoSmithKline Document Number [2015N231308_03](#)].

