The repeated measures logistic regression model will include the following covariates (with example variable names): treatment (ptrtcd), period baseline FEV ₁ (pbli), sex (sex), age (age), treatment period (pernum) and smoking history (supkyr: number of pack years) as fixed effects. A SAS procedure of the following structure will be used:

Statistical Analyses

```
proc genmod data=start descending ;
  class ptrtcd sex pernum subjid / param=ref ;
  model binv = ptrtcd pernum pbli age sex supkyr / dist=bin ;
  repeated subject=subjid / type=unstr corrw;
  estimate "logit FF/VI Vs FP" ptrtcd 1 / exp ;
  ods output Estimates=GEE_or_est ;
run ;
```

Where binv is the binary variable that takes the value 1 if at the given post-challenge time point a subject has an FEV₁ measurement that is $\geq 95\%$ of their pre-exercise FEV₁ measurement and 0 otherwise.

The above code specifies a repeated measures logistic regression model where parameters are estimated using the Generalized Estimating Equation (GEE) method. GEE uses a “working” covariance matrix to model the within-subject dependences during estimation but calculates parameter estimator standard errors using an empirical estimate of the within-subject covariance matrix.

The “estimate” statement estimates the odds ratio of FF/VI compared to FP with 95% confidence limits which are displayed in the SAS output in the “L’Beta Estimate” and “L’Beta Confidence Limits” columns using the “Exp(logit FF/VI Vs FP)” row - these can be found in the “GEE_or_est” dataset produced by the “ods output” statement in the “LBetaEstimate” and “LBetaLowerCL/LBetaUpperCL” columns using the entry in row 2. Note that the quantity displayed in the SAS output in the “Mean Estimate” column is the inverse logit of the FF/VI estimate which is not equal to the odds ratio of FF/VI relative to FP.

Model Checking & Diagnostics

- Refer to [Appendix 11](#): Model Checking and Diagnostics for Statistical Analyses.

Model Results Presentation

- The estimated treatment difference will be displayed as an odds ratio together with the 95% CI and p-value for the treatment comparison along with the number and percentage of subjects in each category. The adjusted treatment ratio and 95% confidence interval will be plotted.

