6	The 12 hour exercise challenge on day 14 of a treatment period (Visit 4/7) occurring on day 11 or earlier of the treatment period i.e. 11 days or less after day 0 of the treatment period (Visit 2/5).	Partial
7	The pre-exercise FEV ₁ prior to the 12 hour challenge on day 14 of a treatment period (Visit 4/7) occurring <11 hours or >13 hours after the previous dose of study medication.	Partial

Apart from any incorrect treatment deviations, all full and partial protocol deviations will be agreed upon prior to unblinding the study.

In addition to the subject level protocol deviations mentioned above, a given FEV₁ measurement must not be within 6 hours after the last use of rescue medication to be included in the Per Protocol analysis of the primary endpoint. Any FEV₁ measurement that was taken within 6 hours after the last use of rescue medication will be considered missing in the Per Protocol analysis of the primary endpoint.

Any FEV₁ measurements that are labelled as 'Unacceptable' will be considered missing for both the Intent-to-Treat and the Per Protocol populations.

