Where minimum post-exercise FEV ₁ is defined in the same way as for the primary endpoint and the same minimum number of non-missing FEV ₁ values are required for the endpoint to be calculated.
Proportion of Subjects With a Post-Challenge FEV₁ No More Than 5% Lower Than Their Pre-Exercise FEV₁
Subjects meeting the criteria will be those who had a post-challenge FEV ₁ \geq 95% of their pre-exercise FEV ₁ . For the time point in question, each subject's post-challenge FEV ₁ as a percentage of their pre-exercise FEV ₁ will be derived as follows:
$\frac{\text{Post Exercise FEV}_1}{\text{Pre-Exercise FEV}_1} \times 100$
If this number is \geq 95% then the subject will have met the criteria.
% of Subjects with a Decrease from Pre-Exercise FEV₁ in 3 Categories
For the time point in question, each subject's percentage decrease from pre-exercise FEV ₁ will be derived as follows:
$\frac{\text{Pre-Exercise FEV}_1 - \text{Post Exercise FEV}_1}{\text{Pre-Exercise FEV}_1} \times 100$
Subjects will then be allocated to one of the 3 categories.
Weighted Mean 0-60 Minutes for % Decrease from Pre-Exercise FEV₁ Following Exercise Challenge
For each time point, the percentage decrease from pre-exercise FEV ₁ will be derived as follows:
$\frac{\text{Pre-Exercise FEV}_1 - \text{Post Exercise FEV}_1}{\text{Pre-Exercise FEV}_1} \times 100$
The weighted mean will then be calculated as the average area under the curve (AAUC) using the trapezoidal rule, and dividing by the relevant time interval. The 0 minute value, coming from the pre-exercise measurement, will be 0 by definition and actual times will be used for all other measurements in the calculation of the AAUC.
The AAUC will be calculated from the first non-missing time point to the last non-missing time point. If one or more observations are missing between two non-missing observations, the value(s) will be linearly interpolated between the two non-missing values.
The AAUC ($t_0 - t_L$ mins) will be calculated as follows:

Secondary and Other Endpoints

$$\text{AAUC}_{(t_0-t_L \text{ mins})} = \frac{\frac{1}{2} \sum_{i=0}^{L-1} (C_i + C_{i+1})(t_{i+1} - t_i)}{t_L - t_0}$$

Where,

i = collected measurement

L = last collected measurement

C_i = result of collected measurement i

t_i = actual time of assessment for collected measurement i

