For the weighted mean over 0-60 minutes, only scheduled planned times (5, 10, 15, 30, 45 and 60 minutes) will be used for the post-exercise time points and only those with an actual time that is less than or equal to 65 minutes after the challenge stop time. The AAUC will only be calculated if there are at least the following non-missing values:

- The 0 hour (pre-exercise) measurement
- A post-exercise measurement with an actual time of ≤ 17 minutes
- A post-exercise measurement with an actual time of ≥ 25 and ≤ 50 minutes
- A post-exercise measurement with an actual time of ≥ 55 and ≤ 65 minutes

If any of these values are missing then the AAUC will not be calculated, and the endpoint will be treated as missing.

ACQ-5

The Asthma Control Questionnaire-5 (ACQ-5) is a five-item questionnaire and there are 7 answers to each question that are associated with the numbers 0-6, where 0 represents no impairment and 6 represents maximum impairment. The ACQ-5 score is the mean of the 5 items and therefore gives a value between 0 (well controlled) and 6 (extremely poorly controlled). The ACQ-5 score will only be calculated if all 5 items of the questionnaire are non-missing.

Physical Activity Measures Assessed by Biosensor

For the physical activity measures assessed by the biosensor, the week 2 time point will be derived using all the available data from the last 7 calendar days prior to, but not including the last scheduled clinic visit of the treatment period (Visit 4/7). For example, if Visit 4 was on the 18th May then the week 2 time point for treatment period 1 would be derived as the average of the non-missing data that is available between the 11th May and the 17th May inclusive.

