10.10. Appendix 10: Multiple Comparisons & Multiplicity

10.10.1. Handling of Multiple Comparisons & Multiplicity

A 2-sided 5% risk associated with incorrectly rejecting any of the null hypotheses (significance level) is considered acceptable for this study. In order to account for multiplicity, the hypothesis test for the FF/VI versus FP treatment comparison using the primary ITT analysis on the primary endpoint will act as a gatekeeper for all other hypothesis tests using the secondary endpoints, where these tests will proceed in the pre-defined order shown below. If a given statistical test fails to reject the null hypothesis of no treatment difference at the significance level of 0.05, then all tests lower down in the hierarchy will be interpreted as descriptive only.

Primary Efficacy Endpoint (Gatekeeper)

1. Test at the 5% level the null hypothesis that the true population difference between the treatment group means in maximal percent decrease from pre-exercise FEV₁ following exercise challenge at 12 hrs post-dose at the end of the 2-week treatment period is zero.

Secondary Efficacy Endpoints

2. If 1 is significant then test at the 5% level the null hypothesis that the true odds ratio between the two treatment groups of recovering to within 5% of pre-exercise FEV₁ at the 30 minute post-exercise time point following the exercise challenge at 12 hours post evening dose is equal to one.
3. If 2 is significant then test at the 5% level the null hypothesis that the true population difference between the treatment group means in maximal percent decrease from pre-exercise FEV₁ following exercise challenge at 23 hrs post-dose at the end of the 2-week treatment period is zero.
4. If 3 is significant then test at the 5% level the null hypothesis that the true odds ratio between the two treatment groups of recovering to within 5% of pre-exercise FEV₁ at the 30 minute post-exercise time point following the exercise challenge at 23 hours post evening dose is equal to one.
5. If 4 is significant then test at the 5% level the null hypothesis that the true population difference between the treatment group means in weighted mean 0-60 minutes for percentage decrease from pre-exercise FEV₁ following the exercise challenge at 12 hrs post-dose at the end of the 2-week treatment period is zero.

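### Recovery and the weighted mean 0–60 are scored from observed FEV1 with no rule for rescue, so in ITT a subject rescued before 30 minutes can count as recovered

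*SAP*

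**What the plan says.** **Recovery.** SAP 10.6.3: "Subjects meeting the criteria will be those who had a post-challenge" FEV1 at or above 95% of the pre-exercise value. SAP 7.2.2.2 codes the same rule: "Where binv is the binary variable that takes the value 1 if at the given post-challenge time point a subject has an" FEV1 that meets the 95% threshold, and 0 otherwise. This follows Protocol 4.2 and 10.4.1.2, which also define the endpoint by the measured value and do not mention rescue.

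**Weighted mean.** SAP 10.6.3: "only scheduled planned times (5, 10, 15, 30, 45 and 60 minutes) will be used for the post-exercise time points". The other conditions concern timing (up to 65 minutes) and minimum data. The missing-data appendix (SAP 10.7.2) adds nothing on rescue.

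**Rescue.** Protocol 8.3.2.1 says that a subject whose FEV1 falls by 40% or more "following exercise challenge, he/she must receive rescue therapy". Protocol 5.1 and 8.3.1.1 also allow it as needed during recovery. Neither rule is tied to the time of the 30-minute reading.

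**The only rescue rule for FEV1.** SAP 10.1.1: a reading "must not be within 6 hours after the last use of rescue medication to be included in the Per Protocol analysis of the primary endpoint". In contrast, efforts labelled unacceptable "will be considered missing for both the Intent-to-Treat and the Per Protocol populations". Secondary endpoints are analysed in ITT (Protocol 10.4.1.2), and the Per Protocol population is used only for the primary endpoint (SAP 4). The rescue rule therefore never reaches recovery or the weighted mean.

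**Position in the hierarchy.** SAP 10.10.1, step 2 (12-hour recovery): "If 1 is significant then test at the 5% level the null hypothesis that the true odds ratio between the two treatment groups" in recovery equals one. Steps 3 to 6 depend on it.

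**The concern.** The objective is protective effect (Protocol 3.1). Subjects are monitored, with rescue available, until FEV1 returns to 95% of the pre-exercise value, and that is the threshold the endpoint scores as success. Rescue can therefore produce the success. A subject who falls 45% at 5 minutes, is rescued, and reads 96% at 30 minutes scores the same as a subject who barely fell.

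The 12-hour recovery test is directly below the gatekeeper. If it is not significant, both 23-hour tests and both weighted-mean tests become descriptive. If it is significant, a recovery claim may partly reflect the rescue bronchodilator. Only challenges with rescue before the reading are affected.

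There is also a data question. The 6-hour rule needs the time of last rescue, but Protocol 7.1 and 7.10 keep study albuterol/salbutamol out of the eCRF, and Protocol 7.1 has use recorded once a day in a paper diary.

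**Working it through.** **1. The plan's own figure.** The documents size only the primary endpoint. SE = 8 × √(2/56) = 1.512 and 5/1.512 = 3.31; on 54 degrees of freedom the power is 90.1%, as in Protocol Table 5. No recovery, rescue or conversion rate is given for the recovery endpoint. Apart from the 56 pairs and the two-sided 5% level, every input below is an assumption.

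**2. Odds ratio.** Let p be unaided recovery, r the proportion rescued before 30 minutes (all from those who would not have recovered unaided), and c the share of those who then read at least 95%. The observed rate is p + c·r. Baseline: FP 50%, FF/VI 72%, so OR = (0.72/0.28)/(0.50/0.50) = 2.57.

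- *More rescue on FP* (10% vs 3.1%). With c = 0.8: FP 0.580, FF/VI 0.7448, OR = 2.918/1.381 = 2.11. With c = 0.5: 0.550 and 0.7355, OR = 2.781/1.222 = 2.28. Diluted.
- *Equal rescue* (10% each, c = 0.8): 0.58 and 0.80, OR = 4.00/1.381 = 2.90. Inflated.
- *Second baseline*, 50% vs 75%, OR 3.00, c = 1. Rescue 10% FP and 3% FF/VI: (0.78/0.22)/(0.60/0.40) = 2.36. Rescue 10% in each: (0.85/0.15)/(0.60/0.40) = 3.78.

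**3. Power, 50% vs 72%.** Simulation of 56 correlated pairs (latent correlation 0.5), with a two-sided 5% Wald test of the log odds ratio using robust paired variance, like the SAP's GEE without covariates. One common rescue cutoff for both treatments gives the FF/VI rescue rate.

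| Rescue FP / FF/VI | Power, c = 0.5 | Power, c = 0.8 |
|---|---|---|
| none | 83% | 83% |
| 2% / 0.4% | 79% | 77% |
| 5% / 1.3% | 74% | 68% |
| 10% / 3.1% | 65% | 54% |
| 15% / 5.3% | 57% | 43% |

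At c = 0.2 the power is 82%, 80% and 76% at 2%, 5% and 10% FP rescue. Other baselines at 10% FP rescue with c = 0.5–0.8: 40% vs 72%, 99% falls to 86–93%; 60% vs 80%, 80% to 50–62%; 50% vs 65%, 50% to 27–34%. Equal 10% rescue with c = 0.8 gives about 78–79%, so a larger odds ratio need not bring more power.

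**4. Counting rescue as not recovered.** If 0, 2, 5 or 10% of subjects who would have recovered unaided are also rescued before 30 minutes in both arms, power is 83, 80, 76 or 68%. That is below observed-value scoring in some cases (76% against 77–79% at 2% FP rescue) and above it in others (68% against 54–65% at 10%).

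**5. Equal recovery in both arms.** Both scorings reject in about 5.1–5.5% of trials.

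**6. Weighted mean.** Trapezoid over 0, 5, 10, 15, 30, 45 and 60 minutes, divided by 60, for one challenge with a 40% fall at 5 minutes (assumed courses).

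- Rescued, then 15, 5, 0, 0, 0: ½(200 + 275 + 100 + 75)/60 = 5.4%. A slower response (20, 10, 3, 0, 0) gives 7.4%.
- Unaided: 34, 28, 15, 8, 4 gives 17.1%; 38, 35, 25, 18, 12 gives 24.6%.
- Pre-rescue fall carried forward: (100 + 40 × 55)/60 = 38.3%, above either unaided course.

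**7. Timing.** An evening dose at 17:00–23:00 puts the 12 (±1) hour challenge at 04:00–12:00 and the 23 (±1) hour challenge at 15:00–23:00 on the same next day. One diary entry per day has no stated way to show which challenge the rescue followed, or whether it came before 30 minutes.

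**The case against.** **The SAP implements the protocol.** The protocol defines recovery as a rule on a measured value, and the SAP applies it. A reader might infer that the SAP departs from the protocol, or that SAP 2.1 ("There were no changes or deviations to the planned statistical analysis specified in the third amendment of the protocol") is wrong here. The documents do not support that. This part of the objection stands.

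**The limit looks deliberate.** SAP 10.1.1 confines the rescue rule to one analysis and, in the next paragraph, extends the unacceptable-effort rule to both populations. The natural inference is that ITT uses values regardless of rescue. It remains an inference: neither document says so or gives a reason. The 6-hour window also equals the pre-visit withholding period, so the rule is only modest evidence that the authors thought post-challenge rescue invalidates a 30-minute reading, although its wording covers such readings.

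**The composite has its own faults.** Rescue is partly discretionary, so counting it as failure partly measures site habits and can lose power. This stands, and it is why replacing the tested definition outright is debatable.

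**The losses rest on assumed rates.** Also true; with 20% conversion they are small.

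**Rescue times may be captured elsewhere.** A reader might infer that they are not recorded at all. The documents do not show that: guidance for worsening at a challenge is in the SRM, which is not available here, nor is the eCRF. What stands is that neither document names a source.

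**Conclusion.** The gap is real and is clear from the text: in ITT a rescued treatment failure can count as recovered in the first test below the gatekeeper, and the weighted mean has the same gap. Neither document states that this is intended. It should be settled before unblinding, because the remedy is cheap and it bears on whether a recovery claim reflects protection.

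The size cannot be taken from the documents. On the assumed rates, the effect runs from a few points of power at 2% FP rescue to tens of points at 10–15%.

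Three stronger readings are not supported:

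- *That the scoring necessarily works against FF/VI.* More rescue on FP dilutes the odds ratio, but equal rescue can inflate it (2.57 to 2.90, or 3.00 to 3.78). The rates by treatment are not given.
- *That type I error is inflated.* With equal recovery and rescue in both arms, rejection stays near 5%.
- *That the primary result is compromised.* The primary endpoint is a minimum, so the fall that triggers mandatory rescue is already recorded.

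**What to change.** Before unblinding, with the clinical rescue rules unchanged:

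1. **Recovery, all time points.** Pre-specify an analysis in which any bronchodilator given between the end of the challenge and the reading counts as not recovered. Then either (a) make it the tested definition, list it as a change in SAP 2.1, and keep the observed-value version as a sensitivity analysis; or (b) state that the tested analysis uses values regardless of rescue, report the composite beside it, and claim protection-related recovery only if the two agree. Do not copy the set-to-missing rule: it would delete the outcomes of exactly the rescued subjects.
2. **Weighted mean.** Keep observed values as the main analysis. Add a sensitivity analysis carrying the last pre-rescue decrease forward, described as possibly overstating the fall.
3. **Tabulate** rescue before 30 and before 60 minutes by treatment and challenge.
4. **Rescue times.** Reconcile the 6-hour rule with the eCRF instruction and the once-daily diary. Name the source of rescue times at challenges, and state how a challenge is scored when the time is missing.

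**Cost.** SAP text, one line of derivation code, one extra analysis per endpoint and one table; no added subjects or procedures. Option (a) changes the working definition of a hierarchically tested endpoint and must be recorded as such. If times were not captured at challenges already done, a new field cannot recover them, so source notes or the stated fallback would be needed. Subjects rescued at discretion who would have recovered unaided count as failures, so the composite may have lower power.

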10.6.4. Safety

Adverse Events

Adverse events will be coded using the MedDRA coding dictionary, to give a preferred term and a system organ class.
Adverse Events of Special Interest

The adverse events of special interest terms, their subgroups and the preferred terms which will be counted towards each of them will be agreed upon prior to unblinding the study.
Pneumonia and Chest X-rays

A chest x-ray will be considered to be associated with a pneumonia assessment if it was performed within -7 to +14 days of the date of onset. If more than one chest x-ray is within that window then the data displays will use the worst case from the answers to "Was an infiltrate present?" i.e. "Yes" will be taken over "Unknown" and "Unknown" will be taken over "No".

10.7. Appendix 7: Premature Withdrawals & Handling of Missing Data

10.7.1. Premature Withdrawals

Element	Reporting Detail
General	
 Subject study completion is defined in the protocol as completing all phases of the study including the follow-up phone contact. Withdrawn subjects will not be replaced in the study. All available data from subjects who were withdrawn from the study is included in listings and where possible any available data from withdrawn subjects is included in any summaries or analyses

10.7.2. Handling of Missing Data

Element	Reporting Detail
Maximal % Decrease / Maximal Decrease	
 As detailed in Section 10.6.3, the only post-exercise FEV₁ values that will be used will be those recorded against the planned post-challenge time points (5, 10, 15, 30, 45 and 60 minutes) and only those with an actual time that is no more than 65 minutes after the challenge stop time. These endpoints will only be calculated if there are at least the following non-missing FEV₁ values: 
 A post-exercise measurement with an actual time of ≤ 17 minutes A post-exercise measurement with an actual time of ≥ 25 and ≤ 50 minutes If there are not values meeting both of these criteria available then the endpoint will not be calculated and will be treated as missing.
Weighted Mean 0-60 Minutes	
 As detailed in Section 10.6.3, only scheduled planned times (5, 10, 15, 30, 45 and 60 minutes) will be used for the post-exercise time points and only those with an actual time that is less than or equal to 65 minutes after the challenge stop time. The weighted mean will only be calculated if there are at least the following non-missing values: 
 The 0 hour (pre-exercise) measurement A post-exercise measurement with an actual time of ≤ 17 minutes A post-exercise measurement with an actual time of ≥ 25 and ≤ 50 minutes A post-exercise measurement with an actual time of ≥ 55 and ≤ 65 minutes If any of these values are missing then the weighted mean will not be calculated, and the endpoint will be treated as missing.
Physical Activity Measures	
 For the physical activity measures assessed by the biosensor, all time periods including baseline, will be calculated from all available data over the time period of interest. No imputations will be performed on missing data.

Element	Reporting Detail
Assessed by Biosensor	
 A day will only be considered valid if the biosensor was worn for at least 21.5 hours in that day. Any day where the biosensor was worn for less than 21.5 hours will not be used and the data from that day will be considered missing. All time periods including baseline, will be considered missing if less than 3 valid days are recorded in the time-period of interest.
ACQ-5	
 For ACQ-5, all questions must be answered to generate an overall score; if any individual questions are missing then the overall score will be missing.

